TITLE PAGE

Oral Mucositis

Protocol Number: SAN005-01

**A Single-Center, Open-Label, Proof of Concept Trial to Evaluate the
Efficacy, Safety and Tolerability of SAN005 for the Prevention and
Treatment of Oral Mucositis Induced by Radiation Therapy
with or without Concurrent Chemotherapy**

Principal Investigator: [name]., Ph.D.

Co-Principal Investigator: [name].

Sub-Investigators: [name].

[name]., Ph.D.

Study Coordinator: [name], R.N., M.S.N.

Supported by: Santalis Pharmaceuticals

Version Date: 27 January 2015

Study Site: University of Texas Health Science Center at San Antonio

Contact Information: [name]., Ph.D.
Dept. Of Radiation Oncology
[name]
[name]
[contact]
Email: [contact]

Title	A Single-Center, Open-Label, Proof of Concept Trial to Evaluate the Efficacy, Safety and Tolerability Trial of SAN005 for the Prevention and Treatment of Oral Mucositis Induced by Radiation Therapy with or without Concurrent Chemotherapy
Setting and Trial Center(s)	This trial will be a single-center study conducted in the United States
Objectives	
The objectives of this proof of concept trial are:
 
• To evaluate the efficacy of SAN005 when administered to adults for the prevention and treatment of radiation induced oral mucositis• To evaluate the safety of SAN005 when administered to adults for the prevention and treatment of radiation induced oral mucositis• To evaluate the tolerability of SAN005 when administered to adults for the prevention and treatment of radiation induced oral mucositis
Trial Design and Subject Population	
This trial will be a single-center, open-label, proof of concept trial to evaluate the efficacy, safety and tolerability of SAN005 treatment regimen when administered to adults at least 18 years of age for the prevention and treatment of oral mucositis.
 
Subjects will enter the Screening Period once the informed consent process has been completed. Subjects who are scheduled to receive radiation with or without concurrent chemotherapy and meet all of the inclusion criteria and none of the exclusion criteria will be eligible for the study:
 
Once subject eligibility is confirmed the subject will start SAN005 treatment on Day 1 of their radiation treatment. All subjects will receive active medication in the study with the first dose administered on Day 1.
 
Subjects will be instructed on the administration of study medication thrice daily throughout the duration of radiation therapy. Subjects will be evaluated by the physician once a week while receiving radiation therapy and then every other week once their radiation therapy has been completed, until their mucositis has resolved for the Final Study Visit.

Inclusion Criteria

Subjects will be included in the trial if they meet all of the following criteria:

1. Subjects with head and neck cancer involving the oropharynx or oral cavity, who are expected to undergo high dose radiation therapy (i.e., ≥ 60 Gy) that typically results in oral mucositis, with or without concurrent chemotherapy or biologic targeted therapy.
2. At least 18 years of age
3. Estimated survival of at least 6 months.
4. No prior radiation therapy to the head and neck area, and no chemotherapy within the last year except for induction chemotherapy delivered (or to be delivered) prior to the current course of radiation therapy
5. Female subjects of child-bearing potential must agree to use an adequate form of contraceptive (e.g., hormonal, barrier method or abstinence) prior to study entry and for the duration of the trial.
6. Are willing to refrain from using other treatments for oral mucositis until they consult with the study investigator(s).
7. Are able to give written informed consent in a manner approved by the Institutional Review Board and comply with the requirements of the study.

Exclusion Criteria

Subjects will be excluded from the trial if they meet any of the following criteria:

1. Have preexisting mucositis from other causes.
2. Are immunosuppressed or in chronic use of immunosuppressive drugs.
3. Have a known sensitivity to any of the constituents of the test product including sensitivities to sandalwood oil, fragrances or any member of the Compositae family of vascular plants (e.g., sunflowers, daisies, dahlias, etc.).
4. ECOG performance status ≥ 3
5. Unwilling or unable to follow the protocol requirements.
6. Have any condition that in the opinion of the investigator would confound the efficacy, safety and tolerability assessments, such as oral thrush.
7. Have participated in any clinical trial in the previous 30 days.
8. Are pregnant, breastfeeding, or unwilling to practice an acceptable form of birth control during the study.

**Screening –
Pretreatment Period**

Visit 1

Eligible subjects will be asked to read and sign an informed consent form. No study procedures will be conducted until the informed consent form is signed.

The study investigator will review inclusion and exclusion criteria to ensure the subject qualifies for the study.

Subjects who meet all of the inclusion criteria and none of the exclusion criteria will be enrolled, then the following study procedures will be performed:

- Record the subject's demographic data including height, weight PEG tube usage, quality of life questionnaire (QoL) and ECOG performance status
- Review and update the subject's pertinent medical history and current medications
- If the subject is a female of childbearing potential, perform a serum pregnancy test before radiotherapy simulation
- Instruct the subject to return for the next study visit

It is allowed that the above procedures to be completed on separate visits, as long as they are done before initiation of radiotherapy.

Treatment Period

Visit 2: Baseline (Day 1 of treatment or at Validation)

The following procedures will be completed at Visit 2 (Baseline).

- Review and update the subject's medications and PEG tube usage
- Inspect the oral cavity for any abnormalities that could potentially confound study results
- Administer the Numerical Rating Pain Scale (NRPS) as related to mouth pain and pain with swallowing. The NRPS will be recorded daily by the subjects between study visits.
- Administer the QoL Questionnaire
- Provide the subject with the products, directions for use and diary. Be sure to weigh the study medication container(s) to ensure an accurate weight of the unused medication is obtained at Visit 3 and for future comparisons
- Request the subject to complete Day 1 of the diary and review for completeness and accuracy

Visit 3 to 8

Clinic visit with a radiation oncologist once a week till the end of treatment.

All study visits will have a \pm 2 day visit window during the radiotherapy.

- Query for adverse events
- Update concomitant medications and PEG tube usage
- Review the diary for the previous week
- Query for treatment regimen compliance
- Collect the study medication and weigh the study medication to determine usage
- Administer the QoL Questionnaire
- Administer the Numerical Rating Pain Scale (NRPS) as related to mouth pain and pain with swallowing. The NRPS will be recorded daily by the subjects between study visits
- Inspect the oral cavity and grade mucositis according to the RTOG Scale
- Record the subject's tolerability to the study drug
- Instruct the subject to return for the next study visit with study medication container and diary

Follow-up Period

Visit 9 to 10

Clinic visit with a radiation oncologist every other week after completion of radiotherapy until either mucositis resolves or it reaches Visit 10, whichever is earlier.

All study visits will have a \pm 2 day window during the follow-up period.

- Query for adverse events
- Update concomitant medications and PEG tube usage
- Review the diary for the previous week.
- Query for treatment regimen compliance
- Collect the study medication and weigh the study medication to determine usage
- Administer the QoL Questionnaire
- Administer the Numerical Rating Pain Scale (NRPS) as related to mouth pain and pain with swallowing. The NRPS will be recorded daily by the subjects between study visits.
- Inspect the oral cavity and grade mucositis according to the RTOG Scale
- Record the subject's tolerability to the study drug
- Instruct the subject to return for the next study visit with study medication container and diary

Trial Contacts

Name	Affiliation / Address	Responsibility
Santalis Corporation	[name] ☎ [contact] ✉ [contact]	Sponsor
[name].	Santalis Corporation [name] ☎ [contact] ✉ [contact] e-mail: [contact]	Sponsor Manager and contact for SAEs

Table of Contents

Contents

TITLE PAGE	1
Trial Contacts	6
Table of Contents.....	7
List of Tables.....	9
List of Figures	10
LIST OF ABBREVIATIONS AND DEFINITION OF TERMS	11
1 INTRODUCTION.....	12
1.1 Oral Mucositis	12
1.2 Santalis Oral Mucositis Treatment.....	12

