3. STUDY PLAN

3.1 Overall Study Design

This trial will be a single-center, open-label, proof of concept trial to evaluate the efficacy, safety and tolerability of SAN005 treatment regimen when administered to adults at least 18 years of age for the prevention and treatment of oral mucositis.

Subjects will enter the Screening Period once the informed consent process has been completed. Subjects who are scheduled to receive radiation with or without concurrent chemotherapy and meet all of the inclusion criteria and none of the exclusion criteria will be eligible for the study:

Once subject eligibility is confirmed the subject will start SAN005 treatment on Day 1 of their radiation treatment. All subjects will receive active medication in the study with the first dose administered on Day 1.

Subjects will be instructed on the administration of study medication thrice daily till oral mucositis resolves. Subjects will return to the clinic once a week while receiving radiation and then once every two weeks once their radiation has been completed and then until their mucositis has resolved for the Final Study Visit.

Preliminary Efficacy Evaluation will be the severity of pain rated by the NRPS and mucositis grade by RTOG criteria at Visit 7 (Day 36). Additional secondary efficacy evaluations will include the severity of pain rated by the NRPS and mucositis grade by RTOG criteria at each study visit, frequency of the PEG tube for feeding during the duration of treatment and weight loss from baseline through Visit 5 and 7. The time of mucositis onset and duration will also be used in assessing efficacy. Additional secondary and exploratory endpoints will be outlined in the statistical analysis plan. The overall efficacy is determined by comparing the data to historical controls.

Safety will be assessed by evaluating adverse events (AEs) with respect to severity, duration, and relationship to study drug. In addition tolerability evaluations will be performed at each study visit.

During the active treatment period, subjects will return to the study site according to the study schedule for interim assessments, review of subject dosing diaries, and assessment of concomitant medication and adverse events (AEs).

The study design is summarized in Figure 3-1.

Figure 3-1 **Study Design**

Pretreatment	Treatment		Follow-up
Day 0	Day 1 Baseline	Day 8,15,22,29,36,43 (\pm 2 day, weekly)	Every other week until mucositis resolves or it reaches Visit 10

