6.0 VISIT SCHEDULE AND ASSESSMENTS

6.1 Study Procedures

The visit schedule and assessments are summarized in Table 5-1. A patient will have a maximum of 10 visits: a pretreatment Visit (Visit 1), weekly treatment visits (Visit 2 – 8), and if the mucositis persists, follow-up visits (Visit 9 -10) every other week until the patient's mucositis has resolved which is estimated out to be approximately 9 to 11 weeks after Day 1 treatment initiation.

Source documents will be completed at each patient's visit, and the data captured in the source documents will be subsequently entered into the case report forms (CRFs) by the Investigator or designee.

Table 6–1 Time and Events

Footnotes to Table 1: Time and Events

- ^a Site staff will follow the requirements of the local IRB if required to obtain informed consent from the subjects.
- ^b Only pertinent medical history will be recorded for each subject including smoking history and alcohol intake.
- ^c A serum pregnancy test will be completed for all women of child-bearing potential before radiotherapy simulation.
- ^d Adverse events will be collected after the subject's first treatment and throughout the trial.

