8. STATISTICAL METHODS AND DETERMINATION OF SAMPLE SIZE

8.1 General Considerations for Data Analysis

All statistical processing will be performed using the SAS® system (Version 9.12 or higher). Up to 15 subjects will be enrolled in this study to ensure a minimum of 10 subjects complete the study. The primary efficacy analysis of the study will be the determination of the NPRS from baseline to Visit 7 (Day 36).

Secondary efficacy endpoints will be evaluated using descriptive statistics. No interim or subgroup analyses are planned.

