8.5.4 Efficacy Analysis

The primary data analysis set for efficacy analyses will be the PP defined in Section 8.4.3. The primary analysis will be the determination of the severity and intensity of mucositis from Baseline to Visit 7 (Day 36).

The secondary efficacy endpoints analysis will be summarized using standard statistical methods and outlined in the Statistical Analysis Plan (SAP). In general, categorical endpoints will be tabulated by number, percentage, and a 95% 2-sided confidence interval (exact methodology) will be estimated. Continuous endpoints (i.e., percent change from baseline) may be summarized using descriptive statistics (N, mean, median, standard deviation, and range).

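### Visits 9 and 10 are held only for subjects unresolved at the previous visit, but the by-visit RTOG and pain summaries have no rule for subjects who left follow-up because they resolved

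*Combined protocol and SAP*

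**What the plan says.** **Visit rule.** The synopsis (Follow-up Period) schedules clinic visits "every other week after completion of radiotherapy until either mucositis resolves or it reaches Visit 10, whichever is earlier". Figure 3-1 gives the same stop: "Every other week until mucositis resolves or it reaches Visit 10". Section 6.1 is the most explicit and counts the late visits only "if the mucositis persists, follow-up visits (Visit 9 -10) every other week". Section 6.2.3 also ends follow-up at resolution.

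**Endpoint.** Section 3.1 includes among the secondary efficacy evaluations the "severity of pain rated by the NRPS and mucositis grade by RTOG criteria at each study visit", with no exception for Visits 9 and 10.

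**Analysis.** Section 8.1: "Secondary efficacy endpoints will be evaluated using descriptive statistics". Section 8.5.4 adds that, in general, "categorical endpoints will be tabulated by number, percentage, and a 95% 2-sided confidence interval (exact methodology) will be estimated", and that continuous endpoints may be summarised by mean, median and similar statistics. It leaves the detail of secondary analyses to the SAP.

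**Not stated in the supplied text.** There is no denominator for a by-visit summary after radiation, no carrying forward of a resolved subject as grade 0, and no note that the late visits cover persisting cases only. Resolution itself is not defined on the RTOG scale.

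**The concern.** Attendance at Visits 9 and 10 depends on the outcome measured there. A subject clear at the end of radiation has, under Section 6.1, no Visit 9. A subject found clear at Visit 9 has no Visit 10. If each visit is summarised over those who attended, the best outcomes leave the denominator one visit after they occur.

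At stake is the description of recovery after radiation. Treatment of mucositis, not only its prevention, is a stated objective, and Section 3.1 judges overall efficacy against historical controls. An attendee-based late rate would make SAN005 look worse than the cohort's true state, and the trend from Visit 9 to Visit 10 could point the wrong way. With about 10 analyzable subjects (Section 4.1), a few departures move a percentage a long way.

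**Working it through.** The documents give no resolution rates and no calculation to reproduce, so the rules are compared first and the size is then shown on assumed counts.

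**Notation.** N is the cohort; a, b and c are the numbers unresolved at the end of radiation, at Visit 9 and at Visit 10. Under Section 6.1, a subjects attend Visit 9 and b attend Visit 10. Withdrawals are ignored, and resolved subjects are taken to stay resolved.

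- Visit 9 rate: b/a among attendees, b/N in the cohort. Gap = (b/a)(1 − a/N).
- Visit 10 rate: c/b among attendees, c/N in the cohort. Gap = (c/b)(1 − b/N).
- The attendee rate rises from Visit 9 to Visit 10 when c/b > b/a, that is when ac > b², although the cohort rate cannot rise because c ≤ b.

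**Simple illustration (assumed).** N = 10, b = 4, c = 2. Attendees: 2/4 = 50%. Cohort: 2/10 = 20%. If the two unresolved subjects are grade 2, mean RTOG grade is (2+2+0+0)/4 = 1.0 among attendees and (2+2)/10 = 0.4 in the cohort.

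**Range of assumed scenarios, N = 10** (exact 95% intervals in brackets):

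| a / b / c | Visit 9: attendees vs cohort | Visit 10: attendees vs cohort | Visit 10 gap (points) |
|---|---|---|---|
| 9 / 7 / 4 | 7/9 = 78% vs 70% | 4/7 = 57% (18–90) vs 40% (12–74) | 17 |
| 8 / 5 / 3 | 5/8 = 62.5% vs 50% | 3/5 = 60% (15–95) vs 30% (7–65) | 30 |
| 6 / 3 / 2 | 3/6 = 50% vs 30% | 2/3 = 67% (9–99) vs 20% (3–56) | 47 |
| 5 / 2 / 1 | 2/5 = 40% vs 20% | 1/2 = 50% (1–99) vs 10% (0–45) | 40 |

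The Visit 10 gap runs from 17 to 47 points and the Visit 9 gap from 8 to 20. In the last two rows ac exceeds b² (12 > 9 and 5 > 4). There the attendee rate rises (50% to 67%; 40% to 50%) while the cohort rate falls (30% to 20%; 20% to 10%).

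**Check against the protocol's own timing.** Figure 3-1 puts Visit 8 at Day 43. If radiation ends then, Visit 9 is Day 43 + 14 = 57, which is (57 − 1)/7 = 8 weeks after Day 1, and Visit 10 is Day 71, or 10 weeks. If radiation ends a week later (assumed), the visits fall at 9 and 11 weeks. Section 6.1 expects resolution at about 9 to 11 weeks. On that estimate nearly everyone attends Visit 9, and depletion at Visit 10 depends on how many are clear by week 8 or 9. The Visit 10 gap cannot exceed 1 − b/N: with b = 9 of 10 it is at most 10 points, and with b = 10 it is zero.

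**The case against.** - **The plan does not specify an attendees-only denominator.** A reader might infer that it commits to a biased rate. It does not: Section 8.5.4 speaks in general terms and leaves detail to the SAP, and either set defined in Sections 8.4.2 and 8.4.3 could serve as the denominator. This stands. But using the full set would still need a value for subjects with no visit, and none is given.
- **A reader might infer that the late results describe only non-resolvers.** They do not. The visit at which resolution is found is itself held, so some attendees are grade 0 that day; in the simple illustration 2 of 4 are. The affected group is those unresolved at the previous visit.
- **The Visit 9 effect may be small.** Apart from Section 6.1, the follow-up wording can be read as giving everyone a first post-radiation visit, and the 9 to 11 week estimate implies few early resolvers. The body of Table 6-1 is missing from the text reviewed, so a note there cannot be excluded. This stands, and it limits the Visit 9 part.
- **Other provisions help.** Section 8.5.2 presents attendance at each visit, and Section 3.1 lists duration of mucositis separately. These would expose a shrinking denominator, but they do not correct the by-visit summaries, and duration has no stated estimator or censoring rule.
- **Comparison with historical controls.** A reader might infer that the comparison is invalid because the controls were all seen at a fixed time. The documents do not describe the controls' follow-up, so this is only conditional.
- **PEG use and QoL add little.** Section 3.1 limits the PEG endpoint to the duration of treatment and does not name QoL as an efficacy evaluation.

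**Conclusion.** The point holds as a moderate one about secondary, descriptive results. The stated visit and endpoint rules, followed together without a rule for resolved subjects, drop the best outcomes from the late summaries. RTOG results based on attendees would overstate persisting mucositis, mainly at Visit 10, and pain probably also.

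The size is not known. It was 17 to 47 percentage points at Visit 10 in the four assumed scenarios, and it shrinks towards zero if almost nobody has resolved by Visit 9. These figures assume N = 10, no withdrawals and no relapse.

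A reader might go further and infer that the trial's efficacy conclusion is biased. The documents do not support that: the primary time point is Visit 7 (Day 36), before any conditional visit.

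**What to change.** In Sections 3.1 and 8.5.4, add for Visits 9 and 10:

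1. **RTOG grade.** Count as grade 0 every subject whose follow-up ended because mucositis was recorded as resolved, whether at the end of radiation or at Visit 9. For this analysis, define resolved as RTOG grade 0, so that a subject whose last recorded grade is above 0 does not qualify. Naming only Visit 9 would miss subjects already clear at the end of radiation.
2. **Denominator.** Use all subjects in the efficacy analysis set who have not withdrawn, and show a missed visit in an unresolved subject as missing.
3. **NRPS and QoL.** Label these summaries as subjects with mucositis persisting at the previous visit. Do not impute pain as 0 after resolution.

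The cost is a few sentences and no new data. The downside is that a relapse after resolution is not seen and would be counted as grade 0, so the assumption should be stated with the table. Holding Visit 9 for every subject is optional: it would remove the assumption at that visit, for at most one extra visit per subject already clear.

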1 INTRODUCTION

1.1 Oral Mucositis

Oral mucositis is an acute injury to the mucosal lining of the head and neck region associated with radiotherapy and chemotherapy. The inflammatory response to injury can cause pain and discomfort that result in dysphagia and odynophagia, excessive secretions and associated nausea. Patients often require a temporary feeding tube to go through radiotherapy. The severity of radiation-induced mucositis is associated with the volume of mucosa irradiated, radiation dose and fractionation, concomitant use of chemotherapy, and patient factors such as tobacco and alcohol use, genetic predisposition and comorbidities. It has a negative impact on patients' quality of life and compliance with treatment that often result in unintended radiation treatment breaks. It can also cause weight loss making radiation dose delivery less optimal secondary to significant tissue volume changes. These can unfavorably affect radiotherapy local control rates.

Currently there have been no agents that are clinically proven to prevent radiation-induced mucositis. The management strategies for oral mucositis are mainly supportive care including adequate pain control, use of protective coating agents or devices, feeding tube use to bypass the irradiated oral mucosa for nutrition and hydration, and other symptomatic management strategies.

Topical and systematic administration of analgesics is the most commonly used first-line therapy. There are many oral agents (various mouth rinses or coating devices) for the management of mucositis symptoms, but none have shown convincing benefits in treating radiation-induced mucositis. The FDA has approved several products not as active pharmacologics but as devices to relieve mucositis symptoms. Among those approved are Gelclair, MuGard, Mucatrol, and Caphasol. Other approaches, such as growth factor GM-CSF, Amifostine, antiseptic and antimicrobial agents, and anti-inflammatory agents have been tested but are mostly negative in trials¹.

